### Study Aims

**Overall objective:** Assess the acceptability and side effects of consuming dried moringa leaf powder (MLP) at 3 different doses (1, 2, or 3 teaspoons) daily for 7 days, among UC Berkeley staff employees.

**Specific Aim 1:** Describe the total acceptability score of MLP, and whether it differed by dose group.

**Sub-Aim 1.1:** Describe the average scores for liking the taste, texture, and appearance of foods after adding MLP, and determine whether they differed by the dose group.

**Specific Aim 2:** Describe the total number of days MLP was consumed during the 7-day intervention period, and whether it differed by the assigned dose.

**Specific Aim 3:** Describe the proportion of participants who reported gastrointestinal or other symptoms after consuming MLP and determine whether it differed by dose group.

**Secondary Aim 1:** Describe the rate of reported willingness to continue consuming MLP and whether it differed by dose group.

**Secondary Aim 2:** Determine the average number of teaspoons consumed (daily and total) for each dose group, based on available data (daily consumption reports), and whether the proportion of the assigned dose consumed differed by group.

**Secondary Aim 3:** Determine whether skin carotenoid score (SCS) increased after consuming MLP for one week, and whether the change in SCS differed by dose group.

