**Sociodemographic variables**

Sociodemographic variables (for reporting sample characteristics) include *age* (years), *gender* (Man, Woman, Non-binary, or Other), *Latinx/Hispanic ethnicity* (Yes or No), and *racial/ethnic identity* (White, Black or African American, American Indian or Alaska Native, Asian, Native Hawaiian or Pacific Islander,

PI: [name]  
University of California, Berkeley

Mixed, or Other). For gender, all respondents reported identifying as a man or a woman, so this variable will be analyzed as binary. For racial/ethnic identity, responses from the two questions will be combined to create a single categorical variable, and categories will be collapsed into fewer categories if needed to allow for analysis.

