### Analysis principles

- Outcomes will be analyzed based on a modified intention-to-treat approach, in which 1) participants with missing outcome data will be excluded (i.e. no imputation will be done), and 2) one participant who was erroneously assigned to a different group from what the randomization order prescribed will be analyzed according to the dose they actually received and were instructed to consume.
- Distributions of variables will be described using frequencies and percentages, in the case of categorical variables, mean (SD) or median (IQR) for continuous variables, and one or both of these for ordinal or count variables.
- Classic ANOVA, Welch's ANOVA, or Kruskal-Wallis tests to detect group differences of ordinal, count and continuous variables will be selected based on whether the following assumptions are met:
  - The distribution within each group is approximately normal based on visual inspection of the data and normal probability plots (Classic ANOVA, Welch's ANOVA).
  - Group variances are approximately equal, i.e., the ratio of the largest to the smallest variance is  $\leq 1.5^{1,2}$  (Classic ANOVA).
- Chi Square or Fisher's Exact test will be used to analyze differences by intervention group for categorical variables.
- Significance level will be set at 0.05. Hypothesis testing results will be interpreted in conjunction with effect sizes and overall trends in the data.
- *Missing data*: For outcomes measured only at the final survey, observations from participants who did not complete the final interview will be excluded from analysis (e.g. Aim 1). For other outcomes, including those measured by daily surveys, available case analysis (e.g. cases with data at each daily survey) will be conducted.
- *Outliers*: Distributions of continuous variables will be visually inspected for outliers, and potential outliers will be investigated further for input errors or other explanations. If no rationale for removing the observation is identified, non-parametric rank-based methods will be considered and/or sensitivity analyses will be conducted to determine the effect of removing the outlier on the results.

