### Baseline participant characteristics

Descriptive summary statistics for sociodemographic and other variables will be reported overall and by intervention group. Age and baseline skin carotenoid scores will be summarized as mean (SD) or median (IQR). Gender identity, racial/ethnic identity, and gastrointestinal and other symptoms (any, as well as individual symptoms) reported by participants in the last 24 hours at baseline will be reported as frequency (%).

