### Secondary Analyses

**Secondary Aim 1 (willingness to consume):** We will report the proportion of participants who reported that they were willing to continue taking the MLP overall and by dose, and investigate whether the distribution of responses differed by dose group, using Chi-square tests if sample sizes allow.

**Secondary Aim 2 (consumption amount):** Average daily dose consumed on consumption days, total MLP consumption (tsp) during the intervention period, and the proportion consumed of the assigned dose will be presented as mean (SD) or median (IQR). All descriptive statistics will be reported overall and by intervention group. To investigate whether the proportion of assigned dose consumed differed by dose group, we will conduct one-way ANOVA, Welch's ANOVA or Kruskal-Wallis tests. Line graphs will be generated to visualize individual participant trajectories of the daily amount consumed and response/non-response to the daily surveys.

**Secondary Aim 3 (skin carotenoid score):** We will report baseline and post-intervention distributions of SCS by dose group as mean (SD) or median (IQR). To determine whether SCS changed after consuming MLP for one week, we will present the distribution of pre-post-intervention changes in SCS as mean (SD) or median (IQR), by dose group. To investigate whether the change in SCS differed by assigned dose, we will perform ANOVA, Welch's ANOVA or Kruskal-Wallis tests of the change in SCS. As a sensitivity analysis, if the model assumptions for linear regression can be met, we will model change in SCS by regressing endline SCS on intervention group, while adjusting for baseline SCS in the following linear regression model: *Endline SCS ~ Dose group + Baseline SCS*.

Reference

1. Lowry R. One-Way Analysis of Variance for Independent Samples. Part 1. In:2002.
2. Morgan CJ. Use of proper statistical techniques for research studies with small samples. *American Journal of Physiology-Lung Cellular and Molecular Physiology*. 2017;313(5):L873-L877.

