### **Appendix. Description of Planned Qualitative Analyses**

In this small pilot study, quantitative results will be interpreted together with the following qualitative analyses of free-response interview questions:

- 1. Qualitative Aim 1.** Describe how participants consumed the moringa powder they received and whether there were patterns in response by the dose consumed.
  - a. **Data:** Mode of consumption was assessed at the final interview using the multiple-choice question, "How did you mostly consume the moringa powder?". Answer options included "mixed with cold food", "mixed with hot food", "sprinkled over cold food", "sprinkled over hot food", "mixed with cold drinks/smoothies", "mixed with hot drinks", "mixed with water" or other.
  - b. **Approach:** Open-ended responses will be coded. Responses to this question will be summarized using frequencies.
- 2. Qualitative Aim 2.** Describe what participants liked and disliked most about the moringa powder they received and whether there were patterns in responses by the dose consumed.
  - a. **Data:** In addition to quantitative scales, acceptability was assessed using 2 open-ended questions, which included "What did you like the most about the moringa powder you received?" and "What didn't you like about the moringa powder?". Responses were recorded (typed in) verbatim or near verbatim by the interviewer.
  - b. **Approach:** To qualitatively describe trends in what participants liked most or disliked about MLP, qualitative thematic analysis will be conducted. Open-ended responses will be coded using pre-specified and emergent themes. Visual aids (e.g. word bubbles, hierarchical graphics, etc.) and tables of themes with the frequency reported will be presented.
- 3. Qualitative Aim 3:** Qualitatively describe whether acceptability of MLP differed by the mode of consumption (e.g., in smoothies, sprinkled over food, etc.).
  - a. **Data:** Total acceptability scores, responses from open-ended questions in which mode of consumption was discussed
  - b. **Approach:** To explore whether acceptability of MLP might differ by the mode of consumption, the mean (SD) of acceptability scores will be calculated by reported mode of consumption, and relevant responses to open-ended questions will be summarized.
- 4. Qualitative Aim 4:** Qualitatively report reasons for non-compliance.

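### Secondary Aim 3 (skin carotenoid score): making the baseline-adjusted model the main between-dose analysis, always run, is a cheap and modest efficiency gain over the planned, valid change-score test

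*SAP*

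**What the plan says.** Under Study Aims, Secondary Aim 3 asks, among other things, "whether the change in SCS differed by dose group". In Secondary Analyses, the test for that question is one-way ANOVA, Welch's ANOVA or "Kruskal-Wallis tests of the change in SCS". None of these uses baseline SCS as a covariate.

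The adjusted model comes next, with lower standing: "As a sensitivity analysis, if the model assumptions for linear regression can be met, we will model change in SCS by regressing endline SCS" on dose group with baseline SCS as covariate.

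Three other places bear on the point:

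- Analysis principles gives the rule for choosing among the ANOVA-type tests. Classic ANOVA needs approximate normality and a variance condition: "Group variances are approximately equal, i.e., the ratio of the largest to the smallest variance is" at most 1.5. These criteria are written for the ANOVA family. The SAP does not say how the regression assumptions will be judged.
- Analysis principles also says "Hypothesis testing results will be interpreted in conjunction with effect sizes and overall trends in the data".
- Baseline participant characteristics says "Age and baseline skin carotenoid scores will be summarized as mean (SD) or median (IQR"), overall and by group.

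SCS is measured on days 1 and 8 (Variables, Outcomes), so the covariate is already collected. The Appendix describes the trial with the words "In this small pilot study". No total or per-group number is stated.

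**The concern.** A change score subtracts the whole baseline value, which fixes the baseline slope at 1. If the true slope is below 1, part of any chance baseline difference between small groups stays in the dose contrast. Averaged over randomizations this appears as lost precision. It is one weakness, and imbalance should not be counted as a second harm.

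The adjusted model estimates the slope instead. It still answers the stated question: once baseline is in the model, regressing endline or change on dose gives the same dose coefficients. The SAP itself presents the regression as a way to model change.

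The condition attached to the model also matters. Because results are to be read with effect sizes, a baseline-adjusted dose difference would be useful to report. It can come only from a model that may be dropped on a judgement for which no criterion is given. At stake is some precision and one more informative estimate for one secondary aim. No primary aim depends on it.

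**Working it through.** **Inputs.** From the SAP: three randomized groups, significance level 0.05, and the 1.5 variance-ratio rule. Assumed, because the SAP does not give them: n = 6, 10 or 15 per group (equal groups), rho = 0.7, 0.8 or 0.9, baseline SD 1, and endline SD k = 1.0 or 1.1. The SAP has no power or precision figure to reproduce.

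**Variance of a difference between two dose groups** (N = 3n):

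- Change score: (1 + k² − 2k·rho) × 2/n
- Adjusted: k²(1 − rho²) × (2/n) × (1 + 1/(N − 5)), where the last factor is the cost of estimating the slope

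With k = 1 the ratio, adjusted over change score, is (1 + rho)/2 × (1 + 1/(N − 5)). Example with n = 10 and rho = 0.8: 0.90 × (1 + 1/25) = 0.936. With k = 1.1, n = 10 and rho = 0.8: 1.21 × 0.36 / (2.21 − 1.76) × 1.04 = 0.968 × 1.04 = 1.01.

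| n per group | k = 1.0, rho 0.7 / 0.8 / 0.9 | k = 1.1, rho 0.7 / 0.8 / 0.9 |
|---|---|---|
| 15 | 0.87 / 0.92 / 0.97 | 0.94 / 0.99 / 1.02 |
| 10 | 0.88 / 0.94 / 0.99 | 0.96 / 1.01 / 1.04 |
| 6 | 0.92 / 0.97 / 1.02 | 0.99 / 1.04 / 1.08 |

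Values below 1 favour adjustment. The benefit fades as rho rises, as groups shrink, or if the endline SD is larger.

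**Power against the SAP's own rule.** Simulated trials (40,000 per setting) used bivariate normal data and a linear dose trend sized so that plain change-score ANOVA has 80% power. The SAP rule is ANOVA if the variance ratio is at most 1.5, otherwise Welch; the visual normality step is not simulated. The adjusted model uses ordinary model-based errors. With k = 1, in percent:

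| n per group | SAP rule, rho 0.7 / 0.8 / 0.9 | Adjusted model | Difference (points) |
|---|---|---|---|
| 15 | 78.8 / 79.0 / 78.9 | 85.2 / 83.2 / 81.1 | 6.4 / 4.2 / 2.2 |
| 10 | 77.6 / 77.8 / 78.0 | 84.6 / 82.6 / 80.4 | 7.0 / 4.8 / 2.4 |
| 6 | 75.3 / 75.2 / 75.0 | 83.2 / 80.9 / 78.7 | 7.9 / 5.7 / 3.7 |

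With k = 1.1 the difference is about 3 to 5 points at rho 0.7, 1 to 3 at rho 0.8 and 0 to 2 at rho 0.9.

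**Where the gain comes from.** Even when true variances are equal, the 1.5 rule sends 74%, 82% and 90% of trials to Welch at 15, 10 and 6 per group. The benchmark of 80% splits each gain in two. At n = 10 and rho 0.7, adjustment gives 84.6 − 80 = 4.6 points, and assuming equal variances gives 80 − 77.6 = 2.4. At n = 6 and rho 0.9, adjustment by itself loses 1.3 points (78.7 − 80), and the equal-variance assumption supplies 5.0 (80 − 75.0).

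**Type I error.** With equal variances both approaches sit at about 5%. With residual SDs of 1, 1.5 and 2 and the smallest group the most variable, ordinary adjusted errors give 9.1% (groups of 13/10/7) and 7.6% (18/15/12), against 5.3% and 4.9% for the SAP rule.

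**The case against.** The strongest reply is that nothing here is wrong. The planned test is valid, matches the outcome as defined, and has Welch and rank-based fallbacks. The adjusted model is already written down. Only the order of two analyses, and a condition on the second, are in question, for the third secondary aim of a small pilot. All of this stands, and it is why the point is minor.

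A second reply is that the gain is uncertain. SCS values a week apart may be highly correlated, where adjustment adds little. This also stands, although ordinary adjustment was not below the SAP's rule in any setting above.

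A third is that ordinary errors give up Welch's protection against unequal variances. That is a real cost, and the retained change-score test is there to expose it. Requiring a robust variance such as HC3 is not a clear remedy. At 10 per group with k = 1.1, the HC3 version had about 77%, 75% and 74% power at rho 0.7, 0.8 and 0.9, against about 78% for the SAP's rule.

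Two stronger readings are tempting, and the SAP supports neither. A reader might infer that the change-score test is biased by baseline imbalance; under randomization it is not. A reader might also infer that the order was chosen after seeing results. The SAP was written with some responses in hand, since it reports that "all respondents reported identifying as a man or a woman". That does not show that SCS by dose had been examined.

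**Conclusion.** The point holds as a minor efficiency improvement and not as an error. The SAP leads with the analysis that is usually less precise and makes the adjusted estimate optional.

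Under the assumed 6 to 15 per group, the gain over the SAP's ANOVA/Welch rule is about 6 to 8 power points at rho 0.7 and 2 to 4 at rho 0.9 with equal SDs. It is about 0 to 5 points across rho 0.7 to 0.9 if the endline SD is 1.1 times baseline. Part of the gain, and all of it at high rho in very small groups, comes from assuming equal variances and not from the covariate. The figures rest on assumed n, SD and rho, normal data and equal groups.

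It would go too far to say that the SAP offers no effect size. Change in SCS is summarized by dose group, so an unadjusted difference can be read off. Only the baseline-adjusted difference may go unreported.

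**What to change.** In Secondary Analyses, Secondary Aim 3:

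1. Make the regression of endline SCS on dose group and baseline SCS, with ordinary model-based errors, the main between-dose analysis, and remove the condition on running it.
2. Report adjusted dose differences with 95% CIs.
3. Keep the change-score ANOVA, Welch or Kruskal-Wallis test as the sensitivity analysis. It also guards against unequal variances and non-normality. Do not require HC3.
4. Keep the descriptive pre-post changes by dose group as written.
5. Add a dated entry to the version history stating whether SCS results by dose had been seen before the change. Without it, the swap could look selective.

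No new data are needed, and both analyses are already in the SAP. The costs are one degree of freedom, a linear common-slope assumption that is hard to check in a small trial, model-based errors that are sensitive to unequal variances, and little return if the correlation is high.

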### **Appendix. Description of Planned Qualitative Analyses**

In this small pilot study, quantitative results will be interpreted together with the following qualitative analyses of free-response interview questions:

- 1. Qualitative Aim 1.** Describe how participants consumed the moringa powder they received and whether there were patterns in response by the dose consumed.
  - a. **Data:** Mode of consumption was assessed at the final interview using the multiple-choice question, "How did you mostly consume the moringa powder?". Answer options included "mixed with cold food", "mixed with hot food", "sprinkled over cold food", "sprinkled over hot food", "mixed with cold drinks/smoothies", "mixed with hot drinks", "mixed with water" or other.
  - b. **Approach:** Open-ended responses will be coded. Responses to this question will be summarized using frequencies.
- 2. Qualitative Aim 2.** Describe what participants liked and disliked most about the moringa powder they received and whether there were patterns in responses by the dose consumed.
  - a. **Data:** In addition to quantitative scales, acceptability was assessed using 2 open-ended questions, which included "What did you like the most about the moringa powder you received?" and "What didn't you like about the moringa powder?". Responses were recorded (typed in) verbatim or near verbatim by the interviewer.
  - b. **Approach:** To qualitatively describe trends in what participants liked most or disliked about MLP, qualitative thematic analysis will be conducted. Open-ended responses will be coded using pre-specified and emergent themes. Visual aids (e.g. word bubbles, hierarchical graphics, etc.) and tables of themes with the frequency reported will be presented.
- 3. Qualitative Aim 3:** Qualitatively describe whether acceptability of MLP differed by the mode of consumption (e.g., in smoothies, sprinkled over food, etc.).
  - a. **Data:** Total acceptability scores, responses from open-ended questions in which mode of consumption was discussed
  - b. **Approach:** To explore whether acceptability of MLP might differ by the mode of consumption, the mean (SD) of acceptability scores will be calculated by reported mode of consumption, and relevant responses to open-ended questions will be summarized.
- 4. Qualitative Aim 4:** Qualitatively report reasons for non-compliance.
  - a. **Data:** If participants reported not consuming the MLP for the whole 7 days, they were asked to give their reason for not consuming MLP.
  - b. **Approach:** Responses to this question will be summarized within the text.
